## **15.0 STATISTICAL CONSIDERATIONS**

### **15.1 Study design and Sample size**

This will be an open-label single-arm phase II trial. The primary endpoint of this study is the 1-year overall survival (OS) which will be compared to historical data. *TP53* mutations occur in 10-15% of patients with AML, and tend to occur in older adults. Our power analysis suggests that we need at least 60 total patients enrolled. We anticipate that 500-700 total AML patients will need to be available at enrolling institutions in order to reach the patient goal of 60. Time to complete accrual will be 24 months.

### **15.2 Analysis Populations**

Intent-to-Treat - Defined as all patients who receive at least one dose of decitabine.

Efficacy-Evaluable - Defined as all patients who receive at least one cycle of treatment.

Safety - Defined as all patients with at least one dose of decitabine.

### **15.3 Multicenter studies**

There are multiple centers in this study, however it is not anticipated that any center will accrue enough patients to warrant an analysis by center

### **15.4 Statistical Analysis**

#### **A. Descriptive Analyses**

Patient Disposition: The number of patients discontinued, the reasons for discontinuation, and the number of cycles administered will be summarized.

Demographics and Baseline Characteristics: Descriptive summary statistics will be provided for demographic and important baseline characteristics. For continuous variables, the number of patients, mean, standard deviation, median, minimum and maximum will be provided. For categorical variables, the number and percent of patients in each demographic/characteristic category will be summarized.

## **B. Primary Endpoint Analysis**

The primary end-point of this phase II study is the 1-year survival in primary relapsed/refractory AML patients treated with decitabine.

Overall survival (OS) is defined as the time from enrollment to death due to any cause. For a patient who is not known to be alive at the end of study follow up, observation of OS is censored on the date the patient was last known to be alive (i.e. date of last contact).

## **C. Overall survival analysis**

Kaplan-Meier curves depicting OS in the study population compared to historical control will be generated. Additionally, the median OS and the probability of OS from 1 month to the end of the follow-up period will be reported at pre-specified intervals. The associated 2-sided 90% CIs will be calculated using the complementary log-log transformation method (Collett 1994).

## **D. Interim Analysis**

The estimated duration of the study is approximately 3 years from enrollment of the first patient to the final analysis. An interim analysis for OS will be performed at 1.5-year (where approximately one-fourth of patients will have at least 1-year follow-up if assuming uniform accrual) and the conditional power will be calculated for futility analysis based on the accumulated data. Conditional power is defined as the projected power to reject the null hypothesis (that treatment of *TP53*-mutated AML patients with relapsed/refractory disease is associated with 1-year survival of 25%) at the end of the study given the data accrued up to the interim analysis. Therefore, a small value of conditional power indicates a highly likely, if not inevitable, conclusion of negative finding given the current data. If conditional power of 0.3 or less is obtained at the interim analysis, an early termination due to futility will be recommended.

## **E. Secondary Clinical Endpoints Analyses**

The principal measurement of toxicity will be a measure of the total number hospitalized days during the first 60 days of therapy.

**CRc rate** will be analyzed based on the ITT population. The remission rate and its 2-sided 90% confidence interval (CI) will be summarized.

**Event-free survival:** EFS will be analyzed using Kaplan-Meier methodology and Kaplan-Meier plots will be provided using the ITT analysis set. The median EFS and its 2-sided 90% CI using the complementary log-log transformation method (Collett 1994) will be calculated.

**Leukemia-free survival:** LFS will be analyzed using Kaplan-Meier methodology

and Kaplan-Meier plots will be provided using the ITT analysis set. The median LFS and its 2-sided 90% CI using the complementary log-log transformation method (Collett 1994) will be calculated.

**Time to leukemia relapse:** TTCR will be summarized using descriptive statistics.

The time to stem cell transplant, the proportion of patients who are able to undergo transplantation, and the average number of hospital days during cycles 1 and 2, will also be documented. The association between response and clinical characteristics (morphologically evident disease -i.e., >5% blasts by cytomorphology- versus molecularly detected disease at the time of enrollment -i.e., disease detected with flow cytometry, cytogenetic, or mutational analysis with  $\leq 5\%$  blasts by cytomorphology-, *de novo AML versus secondary AML versus treatment-related AML*, presence *versus* absence of cytogenetic abnormalities in addition to *TP53* mutations, etc.) will be described using contingency tables and compared by Chi-square test or Fisher's exact test as appropriate. The association between survival (OS, EFS, LFS) and clinical characteristics will be described using Kaplan-Meier methods and compared by log-rank test.

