## Glossary of Abbreviations

AE	Adverse event
ALT (SGPT)	Alanine transaminase (serum glutamate pyruvic transaminase)
AML	Acute myeloid leukemia
t-AML	Therapy-related Acute myeloid leukemia
s-AML	Secondary Acute myeloid leukemia
ANC	Absolute neutrophil count
AST (SGOT)	Aspartate transaminase (serum glutamic oxaloacetic transaminase)
BMT	Bone marrow transplant
BM	Bone marrow
CBC	Complete blood count
CNS	Central nervous system
CR	Complete response
CRc	Cytogenetic complete remission
CRi	Complete remission incomplete hematologic recovery
CT	Computed tomography
CTCAE	Common Terminology Criteria for Adverse Events
DNA	deoxyribonucleic acid
DSM	Data and Safety Monitoring
DSMC	Data Safety Monitoring Committee
ECG (or EKG)	Electrocardiogram
EDTA	ethylenediaminetetraacetic acid
FDA	Food and Drug Administration
FISH	fluorescent in situ hybridization
GCP	Good Clinical Practice
HB	Hemoglobin
HHS	Department of Health and Human Services
HI	Hematologic improvement
HIV	Human Immunodeficiency Virus
HRPO	Human Research Protection Office (IRB)
IRB	Institutional Review Board
ITT	Intention to Treat
MDS	Myelodysplastic syndrome
mLFS	Morphologic leukemia free state
MM	Multiple myeloma
MPN	Myeloproliferative neoplasm
MRI	Magnetic resonance imaging
NCI	National Cancer Institute
NIH	National Institutes of Health
OHRP	Office of Human Research Protections
ORR	Overall response rate

OS	Overall survival
PBMC	Peripheral blood mononuclear cell
PB	Peripheral blood
PD	Progressive disease
PI	Principal investigator
PR	Partial remission
QASMC	Quality Assurance and Safety Monitoring Committee
RFS	Relapse free survival
SAE	Serious adverse event
SAP	Statistical Analysis Plan
SCC	Siteman Cancer Center
SCT	Stem cell transplant
SD	Stable disease
TSH	Thyroid stimulating hormone
TTLR	Time to leukemia relapse
UPN	Unique patient number
WBC	White blood cell count

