### 2.2 Secondary Endpoints

1. To determine the proportion of responding *TP53* mutated patients (CR, CRi) compared to historical controls (10%-15%)
2. To determine the time to stem cell transplant among subjects who are suitable candidates for transplant and have an identified donor.
3. To correlate response and survival with clinical parameters:
  - morphologically evident disease (>5% blasts by cytomorphology) versus molecularly detected disease at the time of enrollment (disease detected with flow cytometry, cytogenetic, or mutational analysis if ≤ 5% blasts by cytomorphology);
  - *de novo AML versus secondary AML versus treatment-related AML*,
  - presence *versus* absence of cytogenetic abnormalities in addition to *TP53* mutations.
4. To determine the median time to leukemia relapse (TTLR) in non-transplant patients treated with decitabine compared to historical control (6-8 months).
5. To determine the 2-year event free survival after transplant in patients treated with decitabine compared to historical control (18-22%).
6. To determine the median and average number of hospital days during Cycles 1 and 2.

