##### **D. DNA Changes**

Conventional chemotherapies in AML cause early termination of DNA synthesis (cytarabine) or topoisomerase inhibition (daunorubicin) that ultimately converge onto TP53 that, together with CDKN2A sense irreparable DNA damage and ultimately trigger cell cycle arrest and cell death. Therefore, it is not surprising that AML with defective TP53 are resistant to conventional chemotherapeutic agents. The effectiveness of decitabine that we observed in the cohort of patient with *TP53* mutation suggests that decitabine acts through a different, TP53 independent, mechanism. Interestingly, *Tp53* null mice develop normally, thus

suggesting that cell cycle exit via differentiation is intact in these mice. As mentioned in Section 1, treatment with decitabine does not lead to clone eradication. Morphologic blast clearance precedes mutation clearance, with the malignant clone often remaining detectable at low levels over time (Figure 4).

This is consistent with a model in which the proliferating cells of the malignant clone enter terminal differentiation after exposure to the drug, with the remaining quiescent stem cells carrying the mutation remaining dormant and eventually contributing to relapse when challenged to cycle.

[figure not shown]

Figure 4: Kinetics of blast clearance versus clonal burden: bone marrow blast reduction detected by morphology at C1D28 does not correlate with founding clone reduction at the same time-point.

Furthermore, difference in DNA methylation may not result in changes in gene expression. For example, AMLs with mutations in *DNMT3A* that result in significant hypomethylation in specific DNA regions, do not display differences in whole transcriptome compared to AML bearing wild type *DNMT3A*. This could be partially explained by the fact that DNA modifications (i.e. methylation status of gene promoters) are not the only determinant of gene transcription. Histones modifications, such as histones methylation, can alter chromatin structure through changes in the chemical moieties on the nucleosome surface and subsequently affect recruitment of the transcription factor machinery to specific DNA regions, silencing or activating gene transcription independently from promoter methylation.

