## 12.0 MEASUREMENT OF EFFECT

### 12.1 Response assessment

Bone marrow biopsy will be obtained on Cycle 1 Day 28 ± 4, Cycle 2 Day 28 ± 4, and Cycle 3 Day 28 ± 4. The cycle 2 Day 28 collection may be performed at the discretion of the treating physician.

All patients will be assessed for response according to the 2017 ELN AML Recommendations:

*Complete remission (CR)* – Defined as bone marrow blasts <5%; absence of circulating blasts and blasts with Auer rods; absence of extramedullary disease; absolute neutrophil count  $\geq 1.0 \times 10^9/L$  (1,000/ $\mu$ L); platelet count  $\geq 100 \times 10^9/L$  (100,000/ $\mu$ L).

*Complete remission with incomplete hematologic recovery (CRi)*: All CR criteria except for residual neutropenia -  $< 1.0 \times 10^9/L$  (1,000/ $\mu$ L) or thrombocytopenia -  $< 100 \times 10^9/L$  (100,000/ $\mu$ L)

*Cytogenetic complete remission (CRc)* – Defined as morphologic complete remission plus a reversion to a normal karyotype. For this study, reversion of a normal karyotype is defined as no clonal abnormalities detected in a minimum of 20 mitotic cells.

*Morphologic leukemia free state (mLFS)*: Defined as bone marrow blasts <5%; absence of blasts with Auer rods; absence of extramedullary disease; no hematologic recovery required. Marrow should not merely be “aplastic”; at least 200 cells should be enumerated or cellularity should be at least 10%

*Partial remission (PR)* – Defined as all hematologic criteria of CR; decrease of bone marrow blast percentage to 5% to 25%; and decrease of pretreatment bone marrow blast percentage by at least 50%.

*Stable Disease (SD)* – Defined as not meeting the definitions of CR, CRi, PR, PD, or recurrence/morphologic relapse.

*Progressive disease (PD)* – Defined as a clear increase in bone marrow blast count, typically a greater than 50% increase compared with baseline, or new extramedullary disease. Patients with a > 50% increase in peripheral blast count with an increase of the total peripheral white blood cell count to > 10,000/ $\mu$ l should undergo evaluation by bone marrow biopsy to assess for progressive disease. Patients enrolled with a bone marrow blast count < 20% will have > 20% blasts and a > 50% increase compared with baseline.

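### Secondary objective 1 is the CR/CRi proportion, but Section 15.4.E estimates only the cytogenetic CR (CRc) rate, so the objective has no matching estimate or confidence interval

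*Combined protocol and SAP*

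**What the plan says.** Section 2.2, item 1, sets the first secondary objective. Its wording, "mutated patients (CR, CRi) compared to historical controls (10%-15" percent), fixes both the endpoint (CR or CRi) and the historical range.

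Section 15.4.E contains one paragraph that estimates a remission rate. It is labelled CRc rate and says that this rate "will be analyzed based on the ITT population. The remission rate and its 2-sided 90% confidence interval (CI) will be summarized". It gives no reference value and no test.

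The abbreviation is defined twice, consistently. The glossary gives "Cytogenetic complete remission". Section 12.1 reads "Defined as morphologic complete remission plus a reversion to a normal karyotype", and specifies the karyotype condition as "no clonal abnormalities detected in a minimum of 20 mitotic cells". CRi is a separate category in Section 12.1: "All CR criteria except for residual neutropenia" or thrombocytopenia, with no karyotype condition.

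Elsewhere in Section 15.4, response appears only as a classifier. Section 15.4.E cross-tabulates an undefined response against baseline characteristics. Section 15.4.F uses CR/CRi to group patients for molecular comparisons. Section 15.4.G gives no power for any response rate.

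**The concern.** The endpoint named in the objective and the endpoint named in the analysis differ. CRc is the stricter of the two, and the historical 10-15% is attached to CR/CRi. An analyst who follows 15.4.E literally produces no CR/CRi proportion and no interval for it. An analyst who notices the gap must choose the analysis set, the handling of patients with few blasts at entry and the reference value after the data are in hand, in an open-label single-arm trial. A reader who sets the reported CRc rate beside the 10-15% in Section 2.2 would be comparing unlike quantities.

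**Working it through.** The plan states no expected value, sample size or power for either rate, so there is no figure to reproduce. The check has two parts.

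**1. Definitions side by side**

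| | CR/CRi (objective 1) | CRc (15.4.E) |
|---|---|---|
| Marrow blasts below 5%, no circulating blasts, no extramedullary disease | required | required |
| Neutrophil and platelet recovery | not required (CRi counts) | required, through CR |
| No clonal abnormality in at least 20 mitotic cells | not required | required |

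Every CRc is a CR, and every CR counts in CR/CRi, so the CRc rate is at most the CR/CRi rate. Reading the word morphologic in the CRc definition loosely, so as to admit CRi, would not change this bound. Section 1.2 says nearly all *TP53*-mutated patients have complex or monosomy karyotypes, so the karyotype condition is relevant to nearly everyone.

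**2. Illustration of size**

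Inputs: n = 60 (Section 15.4.G), all taken as dosed and therefore in the ITT set (Section 15.2); two-sided 90% interval (Section 15.4.E); upper historical value 15% (Section 2.2). Two inputs are assumed because the documents do not give them: a CR/CRi rate of 30%, and the share *f* of CR/CRi responders who also meet CRc.

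Exact (Clopper-Pearson) 90% limits for x responders: lower = 5th percentile of Beta(x, n - x + 1); upper = 95th percentile of Beta(x + 1, n - x).

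- CR/CRi 18/60 = 30.0%: 20.4% to 41.2%, wholly above 15%.
- CRc with f = 1/2, 9/60 = 15.0%: 8.1% to 24.7%, contains both 10% and 15%.
- CRc with f = 1/3, 6/60 = 10.0%: 4.5% to 18.8%, contains both.

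The lower limit first exceeds 15% at 15/60 (lower limit 16.1%; one-sided tail at 15% is 0.029). At 14/60 it does not (14.7%; tail 0.058).

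The chance of observing at least 15/60, P(X ≥ 15) with X ~ Binomial(60, 0.30 × f):

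| Rate analysed | True rate | P(X ≥ 15) |
|---|---|---|
| CR/CRi | 0.300 | 84% |
| CRc, f = 0.75 | 0.225 | 37% |
| CRc, f = 0.60 | 0.180 | 11% |
| CRc, f = 0.50 | 0.150 | 2.9% |
| CRc, f = 0.25 | 0.075 | under 0.1% |

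The direction follows from the definitions. The size depends entirely on f; with f near 1 the two rates nearly coincide.

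**The case against.** **The plan does not make the biased comparison.** A reader might infer that the trial will test CRc against 10-15% and so be biased against decitabine. Section 15.4.E only summarises the CRc rate; the historical range appears only in Section 2.2, attached to CR/CRi. This objection stands. What the text shows is a missing estimate, and the understatement arises only if someone pairs the two sections.

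**The label may be a slip for composite CR.** The same part of 15.4.E abbreviates time to leukemia relapse as TTCR, where the glossary and Section 2.2 use TTLR, so a slip is possible. But both definitions say cytogenetic, and the Schema, Sections 5.1 and 5.5 and the study calendar notes list CRc beside CR and CRi as its own category. If composite CR was meant, the sentence still needs correcting.

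**The CR/CRi count will exist anyway.** Section 15.4.F needs the classification, and Section 13 asks the monitoring report to list how many participants met each objective. That is fair, but neither supplies a pre-specified estimate with an interval.

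**Clone persistence does not show a large gap.** It is tempting to cite Section 9.1.D ("Morphologic blast clearance precedes mutation clearance, with the malignant clone often remaining detectable at low levels over time") as evidence that CRc will be far below CR. That passage, and the residual levels of 0.2-5% in Section 1.2, concern mutations found by sequencing. A 20-cell karyotype is a much coarser test, so the size of the gap is not established. Nor do the documents settle that a patient with a normal karyotype at entry cannot be CRc: the 20-cell condition could be met.

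**A plain CR + CRi rate could err the other way.** Section 3.1 admits patients on flow cytometry, cytogenetics or a persistent mutation alone. Those with fewer than 5% blasts already meet the marrow-blast part of CR/CRi before treatment, and counting them as responders could inflate the rate. This stands and shapes the fix.

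**Conclusion.** The mismatch holds on the text: objective 1 is CR/CRi, the only remission rate estimated is cytogenetic CR, and no section plans an estimate or interval for CR/CRi. CRc cannot exceed CR/CRi. The gap could be negligible or, as in the assumed half-and-half case, enough to move the point estimate from 30% to 15% and bring the historical range inside the interval. The stronger claim, that the plan builds in a biased test against decitabine, is not supported. The effect is confined to a secondary endpoint; the primary OS analysis is unaffected.

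**What to change.** In Section 15.4.E, replace the CRc rate with the CR + CRi rate in the ITT set, with its two-sided 90% CI, read against the 10-15% range of objective 1. Keep CRc as a separate descriptive rate.

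Add that the CR/CRi rate is also reported in patients with more than 5% marrow blasts at entry, a subgroup that Section 2.2, item 3, already defines, and that the historical comparison is made there. This assumes that the historical 10-15% refers to patients with morphologic disease; the documents do not say, and the sponsor should confirm it. The sentence should also state by when response is counted.

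The cost is one or two sentences and no new data: entry marrow, follow-up morphology, cytogenetics and blood counts are already collected (Section 5.1). The comparison will be less precise than with all 60 patients, by an amount that depends on how many enter with 5% blasts or fewer, which the documents do not project.

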### **5.0 INVESTIGATION PLAN**

#### **5.1 Summary**

See Section 10 for synoptic table.

Patients will receive decitabine 20 mg/m^2/day as a 1-hour infusion on consecutive days 1-10 of each 28-day cycle. Decitabine dose will be calculated on baseline weight (obtained within a week of the start of cycle 1). Decitabine dose should be recalculated for weight changes above or below 10% from baseline weight

Patients with clinical evidence of progressive disease or relapse (see Section 12 for definitions) should undergo a bone marrow biopsy to evaluate for progression.

After 2 cycles, patients with progressive disease or relapse (a clear progression with at least >20% bone marrow blasts and an increase of at least 50% from prior biopsy) should be removed from protocol and proceed to salvage treatment according to center preference.

Transplant eligible patients with PR after 3 cycles, may be removed from protocol and proceed to salvage treatment or transplant according to center preference.

Transplant eligible patients with a suitable donor who achieve mLFS, CR, CRc, or CRi, may proceed to transplant after at 3 cycles (Section 5.5).

Transplant ineligible patients with CR, CRc or CRi, PR will continue on maintenance doses (see below and Section 6.3) until progression or death, whichever occur first.

Transplant ineligible patient with SD after cycle 4 may be removed from protocol and proceed to alternative treatment or continue on protocol according to treating physician's preference.

After Cycle 1, patients with blast counts < 5% may reduce decitabine dose from 20 mg/m^2/day x 10 days to 20 mg/m^2/day x 5 days.

For all other patients, after Cycle 2, decitabine administration dose will be decreased to 20 mg/m^2/day for 5 consecutive days (Days 1-5) every 28 days (unless otherwise specified) to limit myelosuppressive toxicity.

Peripheral blood sampling and bone marrow biopsies with aspirate will be performed pre-study, on Cycle 1 Day 10 ± 2, Cycle 1 Day 28 ± 4, on Cycle 2 Day 28 ± 4, on Cycle 3 Day 28 ± 4, and at progression or relapse. Patients will provide a skin biopsy sample pre-study; a buccal swab can be performed for patients who decline skin biopsy. A buccal swab will be collected on Cycle 2 Day 28 ± 4.

Following Cycle 3, bone marrow biopsies should be performed at the discretion of the treating physician to assess for response and for relapse or progression.

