### **5.5 Transplantation**

Patients in mLFS, CR, CRc, or CRi who are considered fit for stem cell transplantation and who have an appropriate donor will undergo stem cell transplantation per treating physician recommendations. Haploidentical and allogenic transplantation may be utilized. Myeloablative and non-myeloablative protocols may be utilized per institutional protocols. Patients will be considered on study through day of transplant and will be followed for overall survival.

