*Recurrence/morphologic relapse* - Defined as relapse following complete remission is defined as reappearance of blasts in the blood or the finding of  $\geq$  5% blasts in the bone marrow, not attributable to any other cause. New dysplastic changes is considered relapse. If there are no blasts in the peripheral blood and 5-20% blasts in the bone marrow, bone marrow biopsy should be repeated in > 1 week to confirm relapse.

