#### **B. Duration of Remission and Relapse-free Survival for Patients Having Complete Remission**

Duration of complete remission is defined as the interval from the date that complete remission is documented to the date of recurrence, death due to any cause, or loss to follow-up.

Relapse-free survival is defined only for those patients achieving a CR or CRi. It is defined as the interval from the date of first documentation of a leukemia-free state to the date of recurrence, death due to any cause, or loss to follow up.

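### Time to leukemia relapse is set against a 6-8 month control median, but its only planned analysis is descriptive statistics, with no start date, censoring rule, death rule or definition of non-transplant

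*Combined protocol and SAP*

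**What the plan says.** Section 2.2, item 4, sets the objective: "To determine the median time to leukemia relapse (TTLR) in non-transplant patients treated with decitabine compared to historical control (6-8 months"). The whole of the analysis text, in Section 15.4.E, is that "TTCR will be summarized using descriptive statistics". The glossary and Section 2.2 abbreviate the endpoint as TTLR; TTCR appears in neither.

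The neighbouring entries in Section 15.4.E are fuller. "EFS will be analyzed using Kaplan-Meier methodology and Kaplan-Meier plots will be provided using the ITT analysis set", and "LFS will be analyzed using Kaplan-Meier methodology"; both also get a median with a two-sided 90% confidence interval.

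Section 12.1 says that "relapse following complete remission is defined as reappearance of blasts in the blood" or a marrow finding, but gives TTLR no start date, censoring rule or rule for death without relapse. The nearest defined endpoint, duration of complete remission in Section 12.1.B, runs "to the date of recurrence, death due to any cause, or loss to follow-up", so loss to follow-up is listed there as an end date and not as a censoring time.

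On transplant, Section 5.5 says that fit patients in mLFS, CR, CRc or CRi with a donor "will undergo stem cell transplantation per treating physician recommendations", and Section 5.1 that such patients "may proceed to transplant after at 3 cycles". Non-transplant is not defined.

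**The concern.** This is a time-to-event median with a benchmark, yet nothing says how patients without a relapse enter it. Some remissions will be ongoing at the final analysis, and some patients will die in remission or be lost. Time to relapse is observed only in those who relapse, so the simplest descriptive summary uses relapsers alone and favours short times.

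The population raises a second problem. Transplant is decided after baseline and depends on response. If non-transplant means never transplanted, candidates who relapse before transplant stay in the group and those who remain in remission leave it.

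At stake is whether the comparison in objective 4 can be interpreted: a real lengthening of remission could be reported as no different from 6-8 months.

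**Working it through.** The 6-8 months is cited from an outside source without inputs, so there is no plan figure to reproduce. The check asks what different summaries would return for a known true median M.

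**Inputs from the documents.** Accrual 24 months (15.1); final analysis about 36 months after first enrolment (15.4.D). Follow-up from entry is therefore 36 − 24 = 12 to 36 months. Section 1.3.B gives a median time to response of 3 months, which leaves 9-33 months after response.

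**Assumptions.** Exponential time from response to relapse, λ = ln 2 / M; follow-up C uniform on 9-33 months; where used, deaths in remission at 0.02 per month; 30% or 50% of responders are transplant candidates, transplanted uniformly 1-4 months after response. The documents give no values for the death rate, candidate share or transplant timing after response.

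**1. Median among observed relapses.** The share with an observed relapse is P = 1 − (e^(−9λ) − e^(−33λ)) / (24λ). Nobody is censored before 9 months, so the median x, if below 9, solves 1 − e^(−λx) = P/2.

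| True M | λ | P | x = −ln(1 − P/2)/λ | With deaths at 2%/month |
|---|---|---|---|---|
| 6 | 0.1155 | 0.880 | 5.0 | 4.5 |
| 8 | 0.0866 | 0.807 | 6.0 | 5.3 |
| 12 | 0.0578 | 0.678 | 7.2 | 6.3 |

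The last column uses the same formulas with λ + 0.02 in place of λ. A true 12 months falls inside the 6-8 month control range.

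**2. Raw median of all times, censored or not.** With administrative censoring alone it is exact for M below 9: 6.0 and 8.0. For M = 12, e^(−λx)(33 − x)/24 = 0.5 gives x = 10.7. With deaths at 2% a month and M = 8, it is 0.693 / (0.0866 + 0.02) = 6.5.

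**3. Never-transplanted patients, complete follow-up, M = 8.** The share of candidates still in remission at transplant is (e^(−λ) − e^(−4λ)) / (3λ) = (0.917 − 0.707)/0.260 = 0.808.
- 30% candidates: 0.3 × 0.808 = 0.242 leave the group, and 0.758 remain. Half is 0.379, of which 0.3 × 0.192 = 0.058 are candidates who relapsed first. The rest gives 1 − e^(−λx) = 0.321/0.7 = 0.459, so x = 7.1.
- 50% candidates: 0.596 remain; half is 0.298, less 0.096, divided by 0.5, is 0.404, so x = 6.0.

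**4. Transplant-ineligible patients, M = 8.** If eligibility is unrelated to relapse time, the median is 8.0.

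**5. Would Kaplan-Meier cure it?** This was simulated with slightly different assumptions: remission 2 months after first dose, candidates transplanted on average 3 months later, and deaths in remission either absent or with a median of 12 months. Kaplan-Meier in all remitters, censored at transplant, death and data cut, returned the true 6.0, 7.0 and 8.0. Kaplan-Meier after dropping transplanted patients did not: 5.0 for a true 7 with 50% candidates and no deaths. The first estimator also fails if candidates differ in relapse risk: 6.4-6.8 against a true 6.9-7.7 when they relapse later (median 10 against 6 months), and 6.5-8.8 against 5.6-7.5 when they relapse earlier (4 against 8 or 10).

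**6. Precision.** With 20 uncensored times and a true median of 7, the sample median ranges from 4.0 to 11.3 (5th to 95th percentile). A median without an interval says little against 6-8 months.

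**The case against.** A reader might infer that the plan ignores censoring, and that its median is therefore biased low against the control. The documents do not support that as fact.

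- Section 15.4.E names no estimator. It does not say that censored patients will be dropped, and a Kaplan-Meier median can be reported descriptively. A short entry with a wrong abbreviation may simply be careless drafting.
- The loss from 8 to 6.0 needs the relapsers-only reading. On the all-times reading, administrative censoring alone does no harm at 6-8 months, and a true 12 would still show as 10.7.
- Non-transplant may mean transplant-ineligible. The Schema and Sections 5.1 and 5.8 divide patients that way, and the selection then largely disappears.
- TTLR has no start date. Counting from first dose would add the time to remission, about 1-3 months if remission is found at the end of Cycles 1 to 3, and could offset the bias. How the control median was derived is not given; it may carry the same selection. If candidates relapse earlier than others (4 against 10 months, 30% candidates), the raw non-transplant median is 7.9 against a true 7.5, which is slightly high.
- This is a secondary objective with no power or decision rule, and event-free survival, analysed by Kaplan-Meier, already counts recurrence.

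All of this stands as a limit on direction and size. None of it supplies the missing rules: the plan permits summaries that differ by months, on an endpoint compared with a range only two months wide.

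**Conclusion.** The point holds as a gap in specification with a probable, not certain, downward bias. The comparison in objective 4 cannot be interpreted as written, because start date, population, censoring and death without relapse are all open and the one method named handles none of them.

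Under the stated assumptions, a relapsers-only median understates a true 8 months by about 2 months and a true 12 by nearly 5. An all-times median is correct at 6-8 months with administrative censoring alone, and about 1.5 months low at a true 8 with deaths at 2% a month. Restriction to the never-transplanted costs a further 1 to 2 months at a true 8; restriction to the transplant-ineligible costs little or nothing. These sizes rest on exponential times and on assumed death and transplant rates. Primary 1-year overall survival and its power do not depend on this endpoint. The change should be made, but the trial's main conclusion does not turn on it.

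**What to change.** In Section 15.4.E, replace the descriptive summary of time to relapse with:

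- TTLR measured from first documented CR or CRi to relapse as defined in Section 12.1, censored at last disease assessment and at transplant;
- a Kaplan-Meier median with a two-sided 90% confidence interval, as for event-free survival;
- a cumulative incidence of relapse with death in remission as a competing event.

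State whether non-transplant means transplant-ineligible. If it does not, analyse all CR/CRi patients with censoring at transplant, and note that this assumes transplant is unrelated to relapse risk; step 5 shows the error if that fails. Analysing all responders also changes the population named in Section 2.2, so the objective should be reworded to match. Correct TTCR to TTLR.

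The cost is a few sentences, one more analysis and one stated assumption. Response, progression and death dates and subsequent therapy are already to be recorded (Sections 5.1.J and 11.0).
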